7 RESEARCH METHODS

7.1 Study Design

This will be a long-term, observational, prospective, and voluntary participation registry-based study designed to collect and assess real-world data on participants with ALGS chronically treated with odevixibat.

The study population will comprise participants with ALGS treated with odevixibat enrolled into the registry-based study. Participants who started odevixibat treatment before the implementation of the registry-based study may also be enrolled.

As this is an observational study designed to assess real-world data, the decision to prescribe the product must be taken prior to, and independently from, the willingness of the participant to be included in the registry-based study. This decision should be made in accordance with routine/standard clinical practice. The assignment of the participant to a particular therapeutic strategy is not decided in advance by the study protocol but falls within current practice.

Participants will be treated and monitored in accordance with usual medical practice during their participation in this registry-based study. No additional assessments or tests will be required by this protocol. All relevant data collected as part of routine medical care will be captured using the electronic Case Report Form (eCRF) by the investigator and transmitted to the sponsor. If some assessments included in this protocol are not routinely performed by the investigator, the corresponding sections in the eCRF do not need to be completed.

This registry-based study will collect data at Baseline and at each Follow-up Visit. Follow-up Visits are scheduled as per routine clinical practice (expected to occur at least every 6 months or more frequently, based on the investigator's judgement).

The duration of this registry-based study is approximately 5 years. Following enrolment, participants will continue to participate in the study for ≥ 2 years or until the time point of withdrawal of consent, for up to 180 days after last dose of odevixibat (in case of treatment discontinuation), death, the end of data collection, or the sponsor decides to discontinue the study.

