7.2 Setting

7.2.1 Inclusion Criteria

To be included in the registry-based study, the participant should fulfil the following inclusion criteria:

- (1) Diagnosed with ALGS.
- (2) On (or starting) active odevixibat treatment.
- (3) Signed informed consent and assent, as appropriate. Consent/assent from the participant or legal representative should be obtained, as appropriate, before any study data collection is conducted. Participants who turn 18 years of age (or legal age per country) while participating in the study will be required to provide consent for themselves.

PAGE 23 OF 76

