7.2.2 Exclusion Criteria

Participants will not be included in the registry-based study if:

- (1) Currently participating in a clinical trial with odevixibat.
- (2) Currently participating in any interventional clinical trial for ALGS.
- (3) Have any contraindication to odevixibat as per the locally approved label.
- (4) Had liver transplant before enrolment.

Individuals who do not meet the criteria for participation in this registry-based study (screen failure) or who withdraw their consent may be rescreened. Rescreened participants should be assigned a new participant number. The informed consent process is described in Section 7.13.

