7.3.1.1 Primary Endpoints

- Incidence of biliary diversion surgery, liver transplantation, or death in participants with ALGS chronically treated with odevixibat.
- Surgical biliary diversion-free survival, defined as time from the start of odevixibat treatment to the first occurrence of surgical biliary diversion or death.
- Liver transplant-free survival, defined as time from the start of odevixibat treatment to the first occurrence of liver transplant or death.
- Overall survival, defined as time from the start of odevixibat treatment to death.

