7.7 Data Analysis

7.7.1 Analyses Population Definitions

Safety Population: all participants who have taken at least one dose of odevixibat following enrolment.

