7.7.2.1 Evaluation of Primary Endpoint

The incidence of biliary diversion surgery, liver transplantation, or death will be assessed using descriptive statistics. Depending on the data available, event free survival endpoints will be summarized using the Kaplan-Meier method. Median time to event with 2-sided 95% CIs and the first and third quartiles will be reported. Survival curves will be presented as well. In addition, survival probability estimates at 6 months, 12 months, and then every 6 months and the associated 2-sided 95% CIs will be reported.

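### Transplant-free and overall survival are timed from first odevixibat dose, but already-treated participants enter only if alive and untransplanted, so an ordinary Kaplan-Meier curve overstates event-free survival

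*Protocol*

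**What the plan says.** Protocol 7.3.1.1 lists four primary endpoints. The first is a descriptive incidence. The other three are times to event, all with the same origin:

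- The transplant endpoint is worded "Liver transplant-free survival, defined as time from the start of odevixibat treatment to the first occurrence of liver transplant or death".
- The mortality endpoint follows the same pattern: "Overall survival, defined as time from the start of odevixibat treatment to death".
- The diversion endpoint does too: "Surgical biliary diversion-free survival, defined as time from the start of odevixibat treatment to the first occurrence of surgical biliary diversion or death".

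Entry is not tied to that origin. Section 7.1 states: "Participants who started odevixibat treatment before the implementation of the registry-based study may also be enrolled". Inclusion criterion 2 in 7.2.1 reads "On (or starting) active odevixibat treatment", and criterion 3 requires consent or assent. Exclusion criterion 4 in 7.2.2 is "Had liver transplant before enrolment". The only analysis population, in 7.7.1, is "all participants who have taken at least one dose of odevixibat following enrolment".

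Prior biliary diversion is handled differently. Sections 7.2.7.1 and 7.3.2.1 record it with its date, and 7.2.2 does not exclude it.

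For the analysis, 7.7.2.1 says that, subject to the data available, "event free survival endpoints will be summarized using the Kaplan-Meier method", with survival probabilities and 95% intervals at 6 and 12 months and every 6 months after that. It mentions neither delayed entry nor left truncation. The limitations in 7.9 cover missing data and differences between sites, not this selection.

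**The concern.** For someone already on treatment, the interval from first dose to enrolment is free of death and transplant by construction: had either occurred, that person would not be in the registry. An ordinary Kaplan-Meier curve from first dose nevertheless keeps the person in the risk set throughout that interval. The denominators are too large where no event can be observed, so the estimated hazard is too low and the curve too high.

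The error has one direction. More participants do not shrink it, and the planned 95% intervals do not reflect it. It falls most directly on transplant-free and overall survival, which are primary effectiveness results of a single-arm study.

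**Working it through.** The protocol states no expected survival, event count or calculated sample size, so there is no figure of its own to reproduce.

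**Inputs from the protocol**
- US authorisation in ALGS: 13 June 2023 (5.3).
- Start of data collection: planned November 2024 (4). Enrolment closes 3 years later (7.2.4), about November 2027.
- Prior commercial treatment is therefore at most about 17 months (1.4 years) at study start and about 53 months (4.4 years) at enrolment close.
- Follow-up is at least 2 years after enrolment (7.2.4).
- Liver transplant is needed by 15% to 25% during childhood (5.2).

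**Assumptions, because the protocol is silent**
- Constant hazard λ. Spreading 15% and 25% over an assumed 18 years gives −ln(0.85)/18 = 0.9% and −ln(0.75)/18 = 1.6% a year. Hazards of 5% and 10% are added to show the range.
- Already-treated share p = 50%.
- Prior treatment time A uniform on 0 to a, with a = 1.4 or 4.4 years.
- No dropout in the first 2 years after enrolment.

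**Formula.** True survival is S(t) = exp(−λt). With nobody censored before 2 years from first dose, the ordinary Kaplan-Meier estimate at t = 2 tends to

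(1 − p)·S(2) + p·E, where E is the mean of exp(−λ·max(0, 2 − A)).

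- If a ≤ 2: E = [exp(−λ(2 − a)) − exp(−2λ)] / (λa)
- If a > 2: E = [1 − exp(−2λ)] / (λa) + 1 − 2/a

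**Worked case, λ = 0.05.** S(2) = exp(−0.10) = 0.9048.
- a = 1.4: E = (0.9704 − 0.9048)/0.07 = 0.9373. Estimate = 0.5 × 0.9048 + 0.5 × 0.9373 = 0.9210. The gap is 1.62 points, and 1.62/9.52 = 17% of the true 2-year risk.
- a = 4.4: E = 0.0952/0.22 + 0.5455 = 0.9780. Estimate = 0.9414. The gap is 3.66 points, or 38% of the risk.

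**All cases, 2-year event-free survival, p = 50%**

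| Hazard per year | True | Ordinary KM, a = 1.4 | Gap (points) | Ordinary KM, a = 4.4 | Gap (points) |
|---|---|---|---|---|---|
| 0.9% | 98.2% | 98.5% | 0.31 | 98.9% | 0.69 |
| 1.6% | 96.9% | 97.4% | 0.55 | 98.1% | 1.21 |
| 5% | 90.5% | 92.1% | 1.62 | 94.1% | 3.66 |
| 10% | 81.9% | 84.9% | 3.00 | 88.8% | 6.93 |

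The relative understatement of risk is about 17% (a = 1.4) to 39% (a = 4.4) and hardly changes with the hazard. The gap equals p·(E − S), so it is proportional to the already-treated share: half these values at 25%, one and a half times at 75%, zero with none.

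**Check by simulation.** With 400,000 simulated participants per scenario and 2 to 5 years of follow-up, the ordinary curve agreed with these values to about 0.1 point. Kaplan-Meier with risk-set entry at enrolment, on the same clock, returned the true curve to within 0.2 point or better in every scenario.

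**The case against.** **The protocol does not say that participants join the risk set at first dose.** It names Kaplan-Meier and leaves detail to a SAP that is not at hand. Delayed entry is compatible with both the named method and the stated origin. This stands in part: a reader might infer that the reported curves are bound to be biased, and the protocol does not establish that. But it fixes origin, eligibility, population and estimator, and those four followed as written give the wrong answer, with nothing pointing to a correction.

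**The size is assumed.** This stands. The hazard and the already-treated share are not in the protocol, and at the hazards derived from its only background rate the gap is about 1 point or less at 2 years. Treated patients may have a higher hazard, but the document does not show it.

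**Delayed entry costs precision with 30 to 45 participants.** This also stands. In simulations with N = 45, half already treated and up to 36 months of prior treatment, the root-mean-square error at 24 months was 4.8 points for the ordinary curve against 5.4 for delayed entry at 5% a year, and 2.4 against 3.3 at 1.6%. In those settings the bias was below one standard deviation. It still always points the same way, and the reported interval conceals it.

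**Scope.** A reader might infer that all the primary results are biased. The incidence endpoint is descriptive and has no time origin to get wrong. For diversion-free survival only death is fully conditioned out: someone diverted after first dose can still enrol, and the date is known. A reader might also infer a false benefit against natural history, but the protocol plans no such comparison and describes its analyses as descriptive.

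**Conclusion.** The point holds for liver transplant-free and overall survival, and for diversion-free survival fully only through its death component. The direction is certain if any already-treated participants are put into an ordinary Kaplan-Meier from first dose and the hazard is not zero.

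The size is conditional. With half the cohort already treated, the 2-year overstatement runs from about 0.3 points (0.9% a year, up to 1.4 years of prior treatment) to about 7 points (10% a year, up to 4.4 years). The upper values depend on hazards well above those implied by the protocol's childhood transplant figure. At the lower hazards the absolute gap is small beside sampling error, although the proportional understatement of risk is much the same.

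The calculation assumes a constant hazard and uniform prior treatment time. It does not model the loss of people who stopped odevixibat before they could enrol, which the active-treatment criterion also removes and which probably pushes the same way.

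**What to change.** In 7.7.2.1, with matching SAP wording:

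1. Keep time since first odevixibat dose as the time scale, but let each participant enter the risk set at the enrolment (consent) date. Show numbers at risk under each curve.
2. For diversion-free survival, leave participants already diverted between first dose and enrolment out of that risk set, and report those diversions descriptively.
3. Show the same three curves for participants who start odevixibat at or after enrolment.

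In 7.9, add as a limitation that already-treated participants are selected for being alive, on treatment and untransplanted.

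No new data are needed: the odevixibat start date is collected under 7.3.2.8 and the consent date must be in the source documents under 7.8.3. The change is wording only and is best made before the first annual interim report. Its cost is smaller early risk sets and wider intervals, which matter with 30 to 45 participants and should be stated alongside the curves.

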7.3.1.2 Secondary Endpoints

• Growth and development in the form of height and weight (standard-deviation scores).

PAGE 29 OF 76

- Incidence of AEs associated with FSV deficiencies and their possible sequelae.
- Incidence of suspected hepatotoxicity requiring interruption of odevixibat treatment.
- Incidence of bleeding AEs, including events requiring emergency department care, hospitalization, or blood transfusion.
- All AEs, based on incidence, severity grade, causality, outcome, action taken, and seriousness.

7.3.2 **Variables**

Only the data collected as part of routine medical care will be captured using the eCRF by the investigator. If some assessments included here are not routinely performed by the investigator, the corresponding sections in the eCRF do not need to be completed.

Demographic and Baseline Characteristics 7.3.2.1

- Age, sex, weight, height, ALGS genetic variant, date of birth (MM/YYYY), and date of ALGS diagnosis
- General medical or surgical history
- Prior surgical procedures related to ALGS, including but not limited to prior biliary diversion surgery (date and type of surgery) and liver transplantation (date and donor information)
- Laboratory parameters, including ALT, AST, ALP, total bilirubin, direct bilirubin, GGT, INR, albumin, creatinine, sodium, platelet count, serum bile acid levels, and FSV levels. Historical values (the most recent values in the last 9 months prior to the first odevixibat dose) are also to be provided at baseline if available.
- Clinical symptoms: pruritus and sleep disturbance, if (semi-) objective scoring data are available. For non-naïve participants, the most recent values prior to the first odevixibat dose are to be collected.
- Pregnancy or breastfeeding status
- Planned biliary diversion surgery (planned date and indication)
- Listing for liver transplantation (planned date and indication)

7.3.2.2 Prior Medication

The registry-based study will assess the use of prior medications, including dose, frequency, start and end dates, and reasons for prescription, at the Baseline Visit. This includes, but is not limited to, the prior use of rifampicin, UDCA, and/or any other IBAT inhibitors. If the prior medication involves other IBAT inhibitors, any AEs leading to their discontinuation will be documented, including their resolution.

Concomitant Medication and Vitamin Supplementation 7.3.2.3

The registry-based study will assess the use of concomitant medication including dose, frequency, start and end dates, and reason for prescription at the Follow-up Visits if available. This includes but is not limited to current use of odevixibat, rifampicin, and UDCA.

Concomitant vitamin supplementation will also be assessed.

PAGE 30 OF 76

7.3.2.4 Concomitant Surgery

The registry-based study will assess the following data on concomitant surgery (including biliary diversion surgery and liver transplantation as outlined in Section 7.3.1.1) at the Baseline Visit and at the Follow-up Visits if available:

- Surgical procedure name
- Indication
- Reason for concomitant surgery
- Date of surgery
- Type of surgery (for Biliary diversion surgery)
- Donor (for Liver transplantation)

7.3.2.5 Weight and Height

The registry-based study will assess growth and development (in the form of weight and height) for all participants at the Baseline Visit and at the Follow-up Visits (only if clinic visit) if available.

7.3.2.6 Safety Variables

The registry-based study will assess the following safety data from the signing of the informed consent form (ICF):

- Adverse Events (including suspected hepatotoxicity requiring interruption of odevixibat treatment and bleeding events) and Special Situations (including pregnancy or breastfeeding status; Section 9.1.3) until 180 days after the last dose of odevixibat
 - O Note: any change in laboratory values deemed as clinically significant by the investigator will be reported as an AE
- Fat-soluble vitamin levels and FSV deficiency questionnaire
 - Note: the questionnaire will assess FSV deficiencies and possible sequelae of FSV deficiency, including whether participants are refractory to clinically recommended vitamin supplementation. The FSV questionnaire will be included in the eCRF and completed by the investigator (See Section 7.6.1 for details on Data Collection)
- Death (date and cause), irrespective of causality, including date and cause of death

If AEs or their sequelae (any AE, based on the investigator's opinion, not only those assessed as related) persist after the date of odevixibat discontinuation the investigator must ensure that the participant receives appropriate medical follow-up and this should be properly documented in the participant's medical records.

Any parameters collected during the study (e.g. laboratory parameters) may be assessed from a safety perspective.

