Other features associated with ALGS include failure to thrive, short stature, immunodeficiency with recurrent infections, pancreatic insufficiency, delayed puberty, and developmental delays (Diaz-Frias 2023). The clinical presentation of ALGS is extremely variable and even patients from the same family with the same genetic mutation may have different presentations (Kamath 2003).

Approximately 95% of patients with ALGS present with chronic cholestasis, usually within the first 3 months of life (Emerick 2002). Laboratory evaluation of these patients revealed elevated serum bile acids, elevated liver function tests, and conjugated hyperbilirubinemia. Associated symptoms include xanthomas, growth failure, and pruritus. Patients with cholestatic liver disease (including ALGS) are at risk to develop fat soluble vitamin (FSV) deficiencies. Signs and symptoms of FSV deficiency include:

• Vitamin A deficiency: night blindness, blindness, dry eyes, hair loss

PAGE 19 OF 76

- Vitamin D deficiency: osteopenia, fractures, muscle weakness, impaired wound healing
- Vitamin E deficiency: muscle weakness, difficulty walking, tremors, vision problems, poor immune function
- Vitamin K deficiency: bleeding difficulties

A substantial portion (45% to 88%) of patients with ALGS present with severe, intractable pruritus, which can be disabling. Patients with ALGS and their caregivers confirm that pruritus is the most bothersome symptom (Kamath 2018).

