6.2.2 Secondary Objectives

- To evaluate the growth and development of participants with ALGS treated with odevixibat.
- To evaluate the incidence of FSV deficiencies and their possible sequelae in participants with ALGS treated with odevixibat.
- To evaluate the incidence of suspected hepatotoxicity requiring interruption of odevixibat treatment.
- To evaluate the incidence of bleeding events in participants with ALGS treated with odevixibat.
- To assess real-world safety data of odevixibat in participants with ALGS.

PAGE 22 OF 76

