- ^b End of study for participants: the last Follow-up Visit as per routine clinical practice before the planned end of data collection (Section 4), withdrawal of consent, lost-to follow up, or 180 days after treatment discontinuation, whichever comes first. In case of treatment discontinuation, the last Follow-up Visit is recommended to happen onsite approximately 180 days after last dose of odevixibat.
- ^c If the participant is < 18 years of age (or the legal age of consent in the jurisdiction in which the study is taking place), assent and parent or legally authorized representative consent will also be required. Participants who turn 18 years of age (or legal age per country) while participating in the study will be required to provide consent for themselves.
- ^d Including age, sex, date of birth (MM/YYYY), and date of ALGS diagnosis
- ^e Prior medications refer only to medications related to the treatment of ALGS, including but not limited to rifampicin, UDCA and/or other IBAT inhibitors. Treatments used up to 9 months prior to the first odevixibat dose are to be collected (including the dose). If prior medications are discontinued, the date of discontinuation is to be provided. If the prior medication involves other IBAT inhibitors, any adverse events leading to their discontinuation will be documented, including their resolution.
- f Concomitant medications include ALGS and non-ALGS oriented treatments, including but not limited to rifampicin and/or UDCA.
- g Type and dose of to be collected.
- ^h Planned date and indication are to be collected.
- ¹ Includes pruritus and sleep disturbance, if (semi-) objective scoring data are available. For non-naïve participants, the most recent values prior to the first odevixibat dose are to be collected.
- ^j Laboratory parameters include-AST, ALT, ALP, total bilirubin, direct bilirubin, GGT, INR, albumin, creatinine, sodium, platelet count, and serum bile acid levels reported since the prior data collection. At the Baseline visit, historical (the most recent values in the last 9 months prior to the first odevixibat dose) values are also to be provided if available.
- ^k AEs collection begins once the informed consent has been signed and will end 180 days after the last odevixibat dose (unless consent was withdrawn). Special Situations include pregnancy or breastfeeding status and overdose, off-label use, misuse, abuse, occupational exposure, medication error, and lack of effectiveness (Section 9.1.3).

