9 MANAGEMENT AND REPORTING OF ADVERSE EVENTS

9.1 Definitions

9.1.1 Adverse Events

AE Definition

An AE is any untoward medical occurrence in a patient/participant administered a medicinal product and which does not necessarily have a causal relationship with this treatment.

Note: An AE can therefore be any unfavorable and unintended sign (e.g. an abnormal laboratory finding), symptom, or disease temporally associated with the use of the medicinal product, whether or not related to the medicinal product.

Events Meeting the AE Definition

Any abnormal laboratory test results (hematology, clinical chemistry, or urinalysis) or other safety assessments (e.g. electrocardiograms, radiological scans, vital signs measurements), including those that worsen from baseline, considered clinically significant in the medical and scientific judgment of the investigator (i.e. not related to progression of underlying disease).

Exacerbation of a chronic or intermittent pre-existing condition including either an increase in frequency and/or severity of the condition.

New condition detected or diagnosed after study treatment administration even though it may have been present before the start of the study.

Signs, symptoms, or the clinical sequelae of a suspected drug-drug interaction.

Signs, symptoms, or the clinical sequelae of a suspected overdose of either study treatment or a concomitant medication. Overdose per se will not be reported as an AE/SAE unless it is an intentional overdose taken with possible suicidal/self-harming intent. Such overdoses should be reported regardless of sequelae.

For studies involving marketed products in established indications:

The signs, symptoms, and/or clinical sequelae resulting from lack of effectiveness will be reported as an AE or SAE if they fulfil the definition of an AE or SAE.

Events NOT Meeting the AE Definition

Any clinically significant abnormal laboratory findings or other abnormal safety assessments which are associated with the underlying disease, unless judged by the investigator to be more severe than expected for the participant's condition.

The disease/disorder being studied or expected progression, signs, or symptoms of the disease/disorder being studied, unless judged by the investigator to be more severe than expected for the participant's condition.

Medical or surgical procedure (e.g. endoscopy, appendectomy): the condition that leads to the procedure is the AE.

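### Sections 7.3.2.6 and 9.1.1 conflict on whether a disease-related laboratory abnormality is an adverse event, so the AE-based vitamin-deficiency endpoint can run low and vary by site

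*Protocol*

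**What the plan says.** Two sections of the protocol decide whether a laboratory abnormality becomes an AE.

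- **Section 7.3.2.6 (Safety Variables)**, in a note under adverse events: "any change in laboratory values deemed as clinically significant by the investigator will be reported as an AE". It makes no exception for the underlying disease.
- **Section 9.1.1 (Adverse Events)**, in the list of events that are not AEs: "Any clinically significant abnormal laboratory findings or other abnormal safety assessments which are associated with the underlying disease, unless judged by the investigator" to be worse than expected for that participant. A parallel item excludes expected signs, symptoms and progression of the disease, with the same proviso.

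Section 9.1.1 also has a list of events that are AEs. It includes abnormal results "considered clinically significant in the medical and scientific judgment of the investigator (i.e. not related to progression of underlying disease"; the bracket closes there.

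Three secondary endpoints depend on AE recording.

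- The FSV objective in 6.2.2 is "To evaluate the incidence of FSV deficiencies and their possible sequelae in participants with ALGS treated with odevixibat", and its endpoint in 7.3.1.2 is "Incidence of AEs associated with FSV deficiencies and their possible sequelae".
- The bleeding endpoint in 7.3.1.2 is also worded as AEs.
- Suspected hepatotoxicity leading to treatment interruption is not worded as an AE in 7.3.1.2, but 7.3.2.6 collects it as one.

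Section 5.1 states: "Patients with cholestatic liver disease (including ALGS) are at risk to develop fat soluble vitamin (FSV) deficiencies". Section 9.1.4 declares adverse events of special interest not applicable, so no special recording rule arises there.

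Sections 7.2.7.1 and 7.2.7.2 list FSV levels at baseline and follow-up. The laboratory footnote to Table 1 does not. Its list ends with "albumin, creatinine, sodium, platelet count, and serum bile acid levels reported since the prior data collection", and the table's only FSV row is the questionnaire.

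**The concern.** Take a low vitamin level that the investigator finds clinically significant and attributes to cholestasis. Section 7.3.2.6 makes it an AE. Section 9.1.1 says it is not one unless it is worse than expected. Because the FSV endpoint counts AEs, that finding enters the numerator at a site working from 7.3.2.6 and can be left out at a site working from 9.1.1.

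The exclusion falls on the kind of event this endpoint exists to measure, since the protocol presents FSV deficiency as a consequence of the disease. A pooled incidence would then mix two counting rules in unknown proportion, and any loss could only be downward. The analysis plan cannot repair this later: AE status is decided at the site, and an AE that was never entered cannot be tabulated.

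**Working it through.** **Step 1. Do the two rules conflict?**

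| Finding | 7.3.2.6 | 9.1.1 |
|---|---|---|
| Clinically significant laboratory change, not disease-related | AE | AE |
| Clinically significant, disease-related, worse than expected | AE | AE |
| Clinically significant, disease-related, not worse than expected | AE | Not an AE |

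They differ in the third row only, and no text says which prevails.

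**Step 2. Does the bracketed gloss in 9.1.1 settle it?** The gloss equates clinical significance with being unrelated to disease progression. The exclusion list in the same section, however, calls disease-associated findings clinically significant, so the term is used in two ways. If a site did carry the gloss into 7.3.2.6, the sections would agree, but by excluding disease-related vitamin findings everywhere. That would remove the variation between sites and leave the risk of undercounting.

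**Step 3. Which endpoints are exposed?**

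- *FSV deficiency*: directly. Low levels are laboratory values, and the endpoint counts AEs.
- *Suspected hepatotoxicity leading to interruption*: less. Suspicion of toxicity already attributes the event at least partly to the drug, and 7.3.2.8 records reasons for dose modification separately. A liver-test rise put down to the disease could still be left out.
- *Bleeding*: not through the two-rule conflict, because a clinical bleed is not a laboratory value. It meets only the 9.1.1 exclusion of expected disease signs. Section 5.1 mentions bleeding only as a sign of vitamin K deficiency.

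**Step 4. How large could the effect be?** The protocol gives no expected rate and no sample size calculation, so there is no stated figure to reproduce. The only input from the documents is the enrolment goal of 30 to 45 participants (7.5). The other two inputs are assumptions:

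- p = share of participants with a clinically significant FSV abnormality;
- f = share of those left out under 9.1.1.

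Incidence under 7.3.2.6 = p. Incidence under 9.1.1 = p × (1 − f). Clopper-Pearson 95% intervals are in brackets.

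| n | p | f | Under 7.3.2.6 | Under 9.1.1 |
|---|---|---|---|---|
| 30 | 20% | 50% | 6/30 = 20.0% (7.7–38.6) | 3/30 = 10.0% (2.1–26.5) |
| 30 | 40% | 25% | 12/30 = 40.0% (22.7–59.4) | 9/30 = 30.0% (14.7–49.4) |
| 30 | 40% | 50% | 12/30 = 40.0% (22.7–59.4) | 6/30 = 20.0% (7.7–38.6) |
| 30 | 40% | 75% | 12/30 = 40.0% (22.7–59.4) | 3/30 = 10.0% (2.1–26.5) |
| 30 | 60% | 50% | 18/30 = 60.0% (40.6–77.3) | 9/30 = 30.0% (14.7–49.4) |
| 45 | 40% | 50% | 18/45 = 40.0% (25.7–55.7) | 9/45 = 20.0% (9.6–34.6) |

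At p = 40% and f = 50% the choice of rule moves the estimate by 40 − 20 = 20 points. The lower arm of the interval around 40% is 40 − 22.7 = 17.3 points at n = 30 and 40 − 25.7 = 14.3 at n = 45. The shift is thus about as large as the sampling error. With f = 0 there is no shift; with f = 100% the count falls to zero. If sites are mixed, the pooled figure lies between p × (1 − f) and p.

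**The case against.** The strongest reply is that FSV deficiency does not rest on AEs alone. Section 7.7.2.2 plans descriptive statistics on the incidence of FSV deficiencies and, in addition, a table of the related AEs. It also summarises FSV signs and symptoms by visit, with shift tables from baseline. FSV levels and a questionnaire covering deficiency, sequelae and resistance to supplementation are collected whatever the AE status. This stands as a second view, and it limits the harm. It does not repair the endpoint that 7.3.1.2 defines, which remains a count of AEs.

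Section 9.1.1 also keeps a good deal: results that worsen from baseline, exacerbations of existing conditions, and anything judged worse than expected. That too stands in part, but each of these again turns on investigator judgement, and the worsening item carries the gloss about disease progression.

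A reader might go further and infer any of the following, none of which the documents support:

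- *That the contradiction governs all three endpoints.* The 7.3.2.6 note concerns laboratory values only, and 7.3.2.6 expressly names bleeding and suspected hepatotoxicity among AEs.
- *That incidence is undercounted, or that some sites will report almost nothing.* Loss occurs only where 9.1.1 is applied and the finding is not judged worse than expected. How often that will happen is not known.
- *That the most exposed endpoint was a regulator's request.* The amendment log shows an AE-based FSV endpoint already in version 1.0. The FDA-linked changes added the hepatic and bleeding objectives and a description of the FSV questionnaire.

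The Table 1 omission is a separate and smaller matter. Section 7.6.1 calls the table a summary, and FSV levels are listed in several other sections.

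**Conclusion.** The concern holds for laboratory findings. Sections 7.3.2.6 and 9.1.1 give different answers for a clinically significant abnormality that is disease-related and no worse than expected, and nothing in the protocol resolves it. The AE-based FSV endpoint can be undercounted and can vary with the rule a site follows. Suspected hepatotoxicity is exposed to a lesser degree, and bleeding only through the exclusion of expected disease signs.

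The size cannot be derived from the documents. The illustration rests on assumed values of p and f and on every affected participant having a finding that 7.3.2.6 would capture. It shows only that, with 30 to 45 participants, the choice of rule could matter about as much as chance. The analyses are descriptive, so no test is affected; what is at stake is the meaning of a reported safety incidence. The point should be corrected, and wording is enough to do it.

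**What to change.** 1. Reconcile 7.3.2.6 with 9.1.1: state which section governs laboratory findings, and use clinical significance in one sense throughout. Adding a list of exceptions to 9.1.1 alone would leave the two sections in conflict for all other laboratory values.
2. State in 9.1.1 that events belonging to a secondary safety endpoint are recorded as AEs whether or not they are attributed to Alagille syndrome: FSV deficiency and its sequelae, suspected hepatotoxicity, and bleeding events. Keep the existing limit on hepatotoxicity to cases requiring interruption of odevixibat, so that the endpoint is not widened. There is precedent: 9.1.2 already requires every fracture to be reported as serious.
3. Report FSV-deficiency incidence also from the levels and questionnaire already collected, beside the AE count. The derivation can go in the analysis plan.
4. Add FSV levels to Table 1 at baseline and follow-up, to match 7.2.7.1 and 7.2.7.2.

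The cost is amendment wording, one table entry and a derivation in the analysis plan. Sites will make somewhat more AE entries. No new tests are needed, since levels and questionnaire are captured only where they are already part of routine care.
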